6.5 SAFETY ANALYSES

The safety analysis will be performed using subjects in the intent-to-treat population. The safety outcome will be incidence of all treatment-emergent adverse events, where “treatment-emergent” is defined as beginning or worsening after treatment initiation. Incidence of device-related adverse events will also be summarized separately.

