7.1 DEFINITIONS

An adverse event is defined as any new medical problem, or exacerbation of an existing problem, experienced by a subject while enrolled in the study, whether or not it is considered device-related by the investigator. During data analysis the Sponsor will evaluate all reported events and may re-categorize some events as expected treatment effects based on the following definition:

- **Expected Treatment Effect:** Any typical treatment side-effect of Ultherapy® of mild to moderate severity and lasting up to a typical maximum duration (see Figure 7.1.1 and Table 8.1.1).

All reported adverse events should be re-assessed by follow-up contact with the subject every 7 days until resolved.

FIGURE 7.1.1: EVENT REPORTING

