8. RISK ANALYSIS

8.1 POTENTIAL RISKS

This treatment modality was designed to inherently minimize the risk to the subject. However, ultrasound exposure with subsequent heating of the soft tissue could involve the risks listed below:

TABLE 8.1.1: EXPECTED TREATMENT EFFECTS

Expected Treatment Effects	Duration
Bruising/Ecchymosis	Up to 2 weeks
Edema/Swelling	Up to 72 hours
Erythema/Redness	Up to 72 hours
Local Muscle Weakness/Paresis	Up to 6 weeks
Nodules	Up to 4 weeks
Acute Pain	Immediate/momentary (while energy is being delivered) - 2 hours
Skin Burn	Up to 4 weeks
Tenderness/Soreness/Pain/Sensitivity to Touch	Up to 2 weeks
Tingling/Paresthesia/Numbness/Nerve Related Transient Pain	Up to 6 weeks
Welting/Raised Areas of Edema	Up to 1 week

Common risks associated with Ibuprofen include nausea, diarrhea, dizziness, headaches and hypertension. NSAIDs (e.g., Ibuprofen) should not be given to patients who have experienced asthma, urticaria, or allergic-type reactions after taking aspirin or other NSAIDs.

These risks will be minimized or reduced by monitoring the subject during the treatment and observing the skin's response to receiving the treatment. If the treatment is not tolerated, the investigator must stop administering treatment for the subject's safety, and the subject will be followed for adverse events for 365 days.

Previous clinical studies with the Ulthera[®] System have shown that the sensory response was tolerable from the subject's and investigator's perspectives. The discomfort was transient and no subject had any residual pain beyond 30 minutes.

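### Section 6.5 does not say whether adverse events are counted before or after the sponsor re-categorises some as expected treatment effects, or where those effects are tabulated by arm

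*Combined protocol and SAP*

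**What the plan says.** Section 6.5 (Safety Analyses) is short. The population is set by "The safety analysis will be performed using subjects in the intent-to-treat population". The outcome follows: "The safety outcome will be incidence of all treatment-emergent adverse events". One further output is planned: "Incidence of device-related adverse events will also be summarized separately". Expected treatment effects are not mentioned.

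Section 7.1 (Definitions) opens broadly: "An adverse event is defined as any new medical problem, or exacerbation of an existing problem", whether or not the investigator considers it device-related. It then gives the sponsor a discretionary step: "During data analysis the Sponsor will evaluate all reported events and may re-categorize some events as expected treatment effects". To qualify, an event must be a typical side-effect of the treatment, "of mild to moderate severity and lasting up to a typical maximum duration". For the durations, the section points to Figure 7.1.1 and Table 8.1.1.

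Table 8.1.1 (Section 8.1) has ten rows. Skin burn and nodules are listed at up to 4 weeks. "Local Muscle Weakness/Paresis" and "Tingling/Paresthesia/Numbness/Nerve Related Transient Pain" are each listed at up to 6 weeks.

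Sections 2.1 and 6.1 state the objective as non-inferiority of Simulines to Standard transducers in both safety and efficacy.

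**The concern.** The plan creates an event category during analysis, and the analysis section gives it no place. If a re-categorised event no longer counts as an adverse event, it drops out of the treatment-emergent incidence. If it was judged device-related, it also drops out of the device-related incidence. Those are the only two safety summaries planned.

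The events concerned are not all trivial. Under Section 7.6, moderate already means that normal daily activity is affected. A moderate burn lasting under 4 weeks, or moderate weakness lasting under 6 weeks, can therefore qualify. A difference between arms in such events bears directly on the safety half of the objective. As the text stands, a reader of the final report could not tell from the plan whether a low adverse event incidence meant few events or many relabelled ones.

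**Working it through.** **The plan's own figures.** The plan gives no safety rate, precision or power to reproduce. The efficacy sample size is not in dispute and only fixes the arm size used below. With 73% response in both arms, a 15-point margin, one-sided 5% and 80% power:

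n = (1.645 + 0.842)² × 2 × 0.73 × 0.27 / 0.15² = 108.3, so 109 per arm, or 218 in total.

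218 / (1 − 0.16) = 259.5, so 260, or 130 per arm at 1:1.

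Both stated figures (109 and 260) reproduce.

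**The sections side by side.**

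| Question | Where the answer would be | What the text says |
|---|---|---|
| Who re-categorises, and when? | 7.1 | The sponsor, at data analysis, at its discretion |
| Which events qualify? | 7.1 and Table 8.1.1 | Typical side-effects, mild to moderate, within the listed duration |
| Does a re-categorised event stop being an adverse event? | 7.1 | Not stated |
| Are the 6.5 incidences taken before or after this step? | 6.5 | Not stated |
| Where are expected treatment effects tabulated by arm? | 6.5, or elsewhere in 6 | No such table is described in the text |
| Is any Table 8.1.1 effect compared by arm by another route? | 6.4.3.2.7 | Yes: treatment pain on the 0–10 scale, modelled with study group as a factor |

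Two readings are open. On the first, expected treatment effect is a label within the adverse event counts, and nothing is lost. On the second, counts are taken after relabelling, and events within the limits leave both summaries.

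**What the second reading could do (assumed rates).** Suppose a Table 8.1.1 event truly occurs in 5% of Standard and 15% of Simulines subjects, with 130 per arm, and a fraction f of affected subjects is removed equally in both arms. The visible rates are 0.05(1 − f) and 0.15(1 − f). The last column is the chance that a Wald 95% interval for the difference, d ± 1.96 × √[p₁(1 − p₁)/130 + p₂(1 − p₂)/130], excludes zero. It was obtained by summing the exact binomial probabilities over all possible outcomes.

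| f | Visible rates | Expected subjects | Chance interval excludes 0 |
|---|---|---|---|
| 0 | 5% v 15% | 6.5 v 19.5 | 0.80 |
| 0.5 | 2.5% v 7.5% | 3.25 v 9.75 | 0.47 |
| 0.8 | 1% v 3% | 1.3 v 3.9 | 0.19 |
| 0.9 | 0.5% v 1.5% | 0.65 v 1.95 | 0.07 |
| 1 | 0 v 0 | 0 v 0 | none |

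The interval is only a yardstick for visibility. Section 6.5 plans incidence summaries and no formal comparison of adverse events between arms.

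**The case against.** The strongest reply is that nothing is removed. Section 7.1 does not say that a re-categorised event stops being an adverse event, its definition is very wide, and Section 6.5 refers to all treatment-emergent events. Figure 7.1.1, whose title is event reporting, is not shown in the text reviewed and may settle the matter. This reply stands in part. A reader might infer that the plan strips these harms out of the safety analysis, and the documents do not support that. What remains is that the text of Section 6.5 does not choose between the two readings. A re-categorisation step placed at data analysis would also have little purpose if it changed no display.

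A reader might also infer that no listed effect is analysed by arm anywhere in Section 6. That is not so: treatment pain is compared in Section 6.4.3.2.7. That analysis does not reach burns, nodules, paresis or later nerve-related pain.

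Nor do the documents show that the Table 8.1.1 effects are the ones most likely to differ between transducers. Section 1.7.1 reports little or no skin-surface effect in the porcine survival study, with resolution equivalent to conventional transducers. Severe or longer-lasting events cannot meet the definition, and serious events have their own reporting route (Sections 7.4 and 7.5).

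Finally, the data may be incomplete. For acute responses, Section 5.1.5 requires photographs and mentions an adverse event form only for serious events. The schedule of assessments asks for the form only when necessary. This limits what an added table can show, but it does not remove the case for one.

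**Conclusion.** The point holds as an ambiguity with consequences. The plan permits discretionary relabelling during analysis of non-severe events within the Table 8.1.1 limits. The text of Section 6.5 does not say whether its two incidences are taken before or after that step, and describes no table for the relabelled events. If counts are taken afterwards, an arm difference in burns, nodules, paresis or nerve effects within those limits could be absent from the planned safety summaries.

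The size is unknown. The 5% versus 15% illustration (0.80, 0.47, 0.19 and 0.07 with none, 50%, 80% and 90% removed) rests on assumed incidences and assumed removal fractions. It shows the mechanism and should not be read as an estimate for this trial. The conclusion also depends on Figure 7.1.1 not settling the question. The primary efficacy test and sample size are unaffected, but because safety is half of the stated objective, the plan should be changed.

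**What to change.** In Section 6.5:

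1. State that the treatment-emergent and device-related incidences are computed on events as reported by the investigator, before any re-categorisation under Section 7.1. The re-categorised version can be kept as a supplementary display.
2. Add one table of reported expected treatment effects by Table 8.1.1 type and arm, giving number and percent of subjects, maximum severity (Section 7.6) and duration where recorded.

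If Figure 7.1.1 already specifies how these events are reported, Section 6.5 should refer to it and agree with it.

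The cost is a few lines of analysis text and one extra table. The headline adverse event incidence will be higher than after re-categorisation. The table will cover only events that sites reported, and a footnote should say so. Sample size, visits and clinical management do not change.

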7. EVALUATION OF ADVERSE EVENTS

[figure not shown]
7.1 DEFINITIONS

An adverse event is defined as any new medical problem, or exacerbation of an existing problem, experienced by a subject while enrolled in the study, whether or not it is considered device-related by the investigator. During data analysis the Sponsor will evaluate all reported events and may re-categorize some events as expected treatment effects based on the following definition:

- **Expected Treatment Effect:** Any typical treatment side-effect of Ultherapy® of mild to moderate severity and lasting up to a typical maximum duration (see Figure 7.1.1 and Table 8.1.1).

All reported adverse events should be re-assessed by follow-up contact with the subject every 7 days until resolved.

FIGURE 7.1.1: EVENT REPORTING

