4.5 SUBJECT RANDOMIZATION AND TREATMENT GROUP ASSIGNMENT

At the Treatment visit, only qualified study subjects (i.e., signed the IRB-approved consent form and confirmed eligible) will be randomly assigned according to a computer-generated 1:1 randomization to receive Ultherapy® treatment using either the Simulines or Standard transducers.

Randomizations will be stratified by site and will use randomly selected blocks of size 4 and 6 and will be generated by an electronic database in a reproducible fashion and will be provided to the site by electronic data capture the point that randomization occurs.

Enrolled subjects will be randomized to one of two treatment groups. Subjects and the study clinician performing efficacy assessments should remain blinded to the assigned treatment group. All randomized subjects will receive a single, dual depth lower face and neck Ultherapy® treatment. Group A will receive treatment with Standard transducers at EL2. The number of treatment lines in each region currently requiring an odd number of lines will be rounded up to an even number for equivalency between Standard and Simulines (e.g. if 15 lines are required in a region on the Standard transducer treatment map then this will be rounded up to 16 lines to match the 16 lines required on the Simulines map). Group B will receive treatment with Simulines transducers at EL2.

Subjects randomized to Group A will receive an Ultherapy® treatment to the lower face and neck with a total minimum pulse count of 672 pulses (+5%) at the 4.5mm and 3.0mm depths using Standard transducers. Energy levels for each transducer will be set to EL2:

- DS 4-4.5 at 0.9J with pitch of 1.5mm and 17 TCP's per line
- DS 7-3.0 at 0.30J with pitch of 1.1mm and 23 TCP's per line

Subjects randomized to Group B will receive a comparable treatment with a total minimum pulse count of 336 pulses (+5%) using the Simulines transducers at the 4.5mm and 3.0mm. Energy levels for each transducer will be set to EL2:

The assigned treatment group should be documented on the appropriate study-specific data form and study log.

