5.1.4 TREATMENT

All study treatments will be performed by the investigator, sub-investigator, or qualified study staff member (i.e., study treatment clinician as designated by the principal investigator.) The study clinician performing efficacy assessments should remain blinded to the assigned treatment group, and therefore may not perform study treatments.

Ultrasound gel will be applied to the transducer, which will then be placed on the targeted skin surface, and ultrasound image will be obtained. Each area of the proposed treatment will be imaged first with the ultrasound device to ensure coupling between the transducer and skin. During the treatment procedure, the study treatment clinician will place multiple Ultherapy[®] treatment lines close to each other in the selected area, with each treatment line requiring about 3 seconds. When using the Simulines transducer the distance the transducer should be advanced between delivery of treatment lines should be doubled as 2 lines of treatment are laid down simultaneously. It is also recommended that at least 2 to 3 passes are used to deliver all lines in each section to allow for tissue cooling between passes of energy delivery. Treatment lines can be a maximum length of 25mm and will produce a series of thermal coagulative points.

Treatment lines to the area highlighted in (Figure 5.1.3-1) above will be administered as specified by Treatment Group. Energy joules delivered for study treatments will be 0.9J joules [EL2] for the Standard 4-4.5mm transducer and 0.30J [EL2] for the Standard 7-3.0mm transducer. [REDACTED]

All study treatments will begin with the 4.5mm depth. The entire 4.5mm depth treatment will be completed prior to continuing to the 3.0mm depth treatment. Treatment will be delivered in a lined pattern. The subject will be monitored during the treatment.

The time each treatment begins and ends will be captured and recorded on the source documents.

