5.2 SAFETY VARIABLES

Prior to treatment, the subject's medical history will be reviewed, a urine pregnancy test will be performed (if applicable), and a physical examination will be conducted. During Ultherapy[®] treatment, the subject's pain levels will be monitored using a validated Numeric Rating Scale (Attachment D). Average pain scores should be obtained following each region treated and for each transducer used during treatment. The average pain score for the entire region treated by each transducer will be recorded. A script will be used for collecting pain scores.

At each subsequent visit, the subject will be queried about adverse events and changes in concomitant medications, and the treatment area will be visually examined. A second pregnancy screening test will be performed at the 365-day follow-up visit.

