6. STATISTICAL ANALYSIS

6.1 STUDY OBJECTIVE

The objective of this study is to demonstrate that the safety and efficacy of Simulines transducers at Energy Level 2 [EL2] is not inferior to treatment with Standard transducers at Energy Level 2 [EL2] in order to limit the energy level of both types of transducers to a maximum of EL2 for lift indications. To fulfill this objective we will be using the same treatment depths and regions treated as those used in the pivotal study that supported the submental/neck clearance, but at EL2 instead of Energy Level 4 [EL4]. Simulines transducers deliver 2 lines of treatment per pulse (push of the button) versus Standard transducers which deliver 1 line of treatment per pulse.

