6.2 DETERMINATION OF SAMPLE SIZE AND STUDY SUCCESS

A sample size of 260 randomized subjects will be required to account for up to 16% attrition to have 80% power to determine non-inferiority given a response rate of 73% in both randomized groups and a non-inferiority margin of 15%. Response is defined as greater than 20 mm² reduction in neck and submental area from baseline. The study was powered based on the expected response rate of 73% as seen in the pivotal trial supporting the neck/submental lift indication FDA clearance K121700. The observed response rate of the prior pivotal trial (73%) was higher than the minimum response rate required (65%) for success of the supporting trial. Study success will be achieved given a statistically significant determination for non-inferiority for the primary efficacy objective. Statistical significance is determined using a one-sided $\alpha=0.05$.

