6.4.3 EFFICACY ANALYSIS

6.4.3.1 PRIMARY EFFICACY ANALYSES

Subjects included in the analysis: All ITT subjects will be included in the analysis.

Endpoint: Subject response is defined as ≥ 20 mm² reduction in 2D submental area from baseline. The left and right side value at baseline will be averaged to result in the 2D submental area at baseline. The left and right side value at 90 days will be averaged to result in the 2D submental area at 90 days. In the event, only either the left or right side data is available, it will be used. Response will be calculated as baseline – 90 days. The evaluator that determines 2D submental area is blinded to follow-up and study group.

Hypothesis:

H₀: The proportion of responders at 90 days as compared to baseline for the test group is inferior as compared to the control group given a non-inferiority margin of δ , $p_{\text{control}} - p_{\text{test}} \geq \delta = 15\%$.

H_a: The proportion of responders at 90 days as compared to baseline for the test group is not inferior as compared to the control group given a non-inferiority margin of δ , $p_{\text{control}} - p_{\text{test}} < \delta = 15\%$

Sample Size Rationale: The sample size calculation assumes 73% response in both randomized groups. Power was set at 80%, one-sided Type I error controlled at 5%, a non-inferiority margin of 15% and PASS 12 Non-inferiority for two independent proportions using the Z-test with unpooled variance was used. The sample size requires 109 subjects per randomized group to have data necessary to calculate the primary endpoint. The total sample size of 218 was corrected for up to 16% attrition to arrive at 260 subjects randomized in the study.

Primary Statistical Analysis: The primary statistical analysis will be conducted using the observed data in the intent-to-treat patients using the Z-test (unpooled) for two independent proportions. Statistical significance is determined using a one-sided $\alpha=0.05$.

Additional Statistical Analysis: If there are intent to treat subjects with missing data, the analysis as specified in Section 6.4.1 Handling of Missing data will be conducted. The analysis in Section 6.4.1 regarding pooling will be conducted as specified in that section. The analysis will be completed for the subset of per protocol patients.

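### The objective claims that safety is not inferior, but the plan contains no between-arm adverse-event analysis that could support that claim

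*Combined protocol and SAP*

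**What the plan says.** **Objective.** The synopsis, Section 2.1 and Section 6.1 each give the aim as demonstrating that the "safety and efficacy of Simulines transducers at Energy Level 2 [EL2] is not inferior" to Standard transducers at the same energy level. Safety and efficacy share one non-inferiority statement.

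**Success and hypotheses.** Section 6.2 states: "Study success will be achieved given a statistically significant determination for non-inferiority for the primary efficacy objective". The hypotheses, the 15% margin and the sample size in Section 6.4.3.1 all concern the 90-day responder proportion.

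**Safety analysis.** Section 6.5 uses the intent-to-treat population and states: "The safety outcome will be incidence of all treatment-emergent adverse events". Device-related events are summarised separately. No difference between arms, interval, test or margin is given.

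**Related provisions.** Section 5.2 lists pain among the safety variables ("pain levels will be monitored using a validated Numeric Rating Scale"), and Section 6.4.3.2.7 compares pain scores between groups in a two-sided model. Section 2.2 requires a safety report after the first 15 subjects, before enrolment opens at all sites.

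**Re-categorisation.** Section 7.1 states: "During data analysis the Sponsor will evaluate all reported events and may re-categorize some events as expected treatment effects based on the following definition". The definition requires a typical side-effect of mild to moderate severity, within the durations in Table 8.1.1. It also refers to Figure 7.1.1, which is missing from the text available.

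**The concern.** An objective worded as a demonstration of non-inferiority needs three things: a quantity to compare, a margin, and an analysis that can exclude that margin. Efficacy has all three. Safety has only a list of incidences. If the plan is followed as written and efficacy succeeds, the report could state that the whole objective was met, although no planned analysis had compared adverse events between arms.

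The second, lesser question is what the Section 6.5 incidences would contain. Table 8.1.1 lists redness and swelling, but also skin burn, nodules, local muscle weakness and numbness, on which two transducer types could differ. If events that meet the definition were handled differently in the two arms, the comparison would be biased, and a reader could not see this without counts before and after the step.

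**Working it through.** **1. The plan's own calculation covers efficacy only.** Inputs from Section 6.4.3.1: 73% response in both arms, margin 15 points, one-sided alpha 0.05, power 80%, unpooled Z-test, attrition up to 16%.

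n per arm = (1.645 + 0.842)² × 2 × 0.73 × 0.27 / 0.15² = 6.185 × 0.3942 / 0.0225 = 108.4, so 109.

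Total 218; 218 / 0.84 = 259.5, so 260.

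The stated figures reproduce. There is no corresponding safety figure to check.

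**2. Side by side.**

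| Element | Efficacy | Adverse events |
|---|---|---|
| Named in the objective as not inferior | Yes | Yes |
| Hypotheses and margin | Section 6.4.3.1, 15% | None |
| Part of the success rule | Section 6.2 | No |
| Between-arm comparison | Unpooled Z-test | None in Section 6.5 |

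The related provisions do not fill the right-hand column. The pain model has no margin and does not address adverse-event incidence. The 15-subject report is a staging step and is not described as a comparison of arms.

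**3. What an interval could show.** The documents give no expected incidence for this trial, so equal incidences p of 10%, 30% and 50% are assumed. With 260 randomised 1:1 there are 130 per arm; the synopsis says up to 260, so fewer subjects would widen the intervals.

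SE = √(2p(1 − p)/130); 95% half-width = 1.96 × SE; margin excludable with 80% power at one-sided 5% = (1.645 + 0.842) × SE.

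| Assumed p | SE | 95% half-width | Margin excludable |
|---|---|---|---|
| 10% | 0.0372 | 7.3 points | 9.3 points |
| 30% | 0.0568 | 11.1 points | 14.1 points |
| 50% | 0.0620 | 12.2 points | 15.4 points |

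The last column matters only if the sponsor keeps the safety non-inferiority claim.

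**4. Re-categorisation, as illustration only.** If three subjects left the count in one arm and none in the other, the difference would move by 3/130 = 2.3 points. That is 32%, 21% and 19% of the half-widths above (2.31/7.29, 2.31/11.14, 2.31/12.16). The three is arbitrary. A subject leaves an incidence count only if all of that subject's counted events are re-categorised.

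**5. Where masking is stated.** Section 6.4.3.1: "The evaluator that determines 2D submental area is blinded to follow-up and study group". Section 5.1.4: "The study clinician performing efficacy assessments should remain blinded to the assigned treatment group, and therefore may not perform study treatments". No such sentence accompanies the re-categorisation step in the visible text, and Section 4.5 states: "The assigned treatment group should be documented on the appropriate study-specific data form and study log".

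**The case against.** The best defence is that no success decision depends on safety. Section 6.2 ties success to efficacy, and descriptive adverse-event reporting is a common choice when efficacy drives the sample size. This stands as a defence of the analysis, but not of the objective, which promises a demonstration. The conflict is one of wording and can be removed cheaply.

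On re-categorisation, the discretion is narrower than it first looks. The sponsor evaluates all reported events against a written definition, severity is graded in Section 7.6, and Table 8.1.1 sets maximum durations. Severe or longer-lasting events do not qualify, and the reference to some events may simply mean those that do. Figure 7.1.1 may set out the process. All of this stands, which is why the point is secondary and conditional.

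A reader might infer that the sponsor would re-categorise selectively in favour of one arm. The documents show no uneven application and do not suggest it. A reader might also infer that re-categorised events disappear from the safety outcome. Section 6.5 speaks of all treatment-emergent events, which can be read as keeping them. The text leaves the matter open and does not establish exclusion.

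**Conclusion.** The main point holds. The plan cannot support a conclusion that safety is not inferior, because no adverse-event comparison or margin is specified. This rests on the text of Sections 2.1, 6.1, 6.2, 6.4.3.1 and 6.5 and needs no assumed number. It does not affect the efficacy hypothesis, the sample size or the success rule.

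The size is a matter of precision. With 130 per arm and assumed equal incidences, the 95% half-width is about 7 points at 10%, 11 at 30% and 12 at 50%. At 30% to 50% incidence, a safety non-inferiority claim with 80% power would need a margin of about 14 to 15 points, which would itself need justification.

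The re-categorisation point is a request for clarification, subject to Figure 7.1.1. The visible text states no masking to arm and does not settle how re-categorised events are counted. The stronger reading, that the safety results would be biased, is not supported: the three-subject shift is hypothetical and lies well inside each interval.

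**What to change.** 1. **Synopsis, Sections 2.1 and 6.1.** Reword the objective so that non-inferiority refers to efficacy, and safety is described and compared between arms with an interval. Keep the safety non-inferiority claim only if a justified margin is pre-specified.
2. **Section 6.5.** Tabulate by arm, and give the Simulines minus Standard difference in subject incidence with a 95% confidence interval for all treatment-emergent adverse events as reported by investigators, since that is the plan's named outcome. Do the same for device-related events, noting that relatedness (Section 7.2) is judged by the investigator, who may have given the treatment and so know the device (Section 5.1.4).
3. **Section 7.1, unless Figure 7.1.1 already covers it.** Apply the existing definition to every event that meets it, from a listing without arm, transducer type, pulse count (minimum 672 versus 336) or treatment time. State whether re-categorised events stay in the Section 6.5 counts, and show counts by arm before and after.

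The cost is protocol and SAP wording, a few tables and a masked listing. Because arm is on the data form and log, someone separate may be needed to prepare that listing. No new visits or subject data are required. The safety tables will be longer and may look less favourable. One limit remains: acute responses are observed by the treating clinician (Section 5.1.5), so the original reporting is not masked, and the report should say so.
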